## Research Design and Methods

The proposed study is a pilot RCT with multi-method longitudinal assessment (refer to **Figure 1** for an overview of study activities). The study has three primary aims: (1) to assess the feasibility of recruiting Veterans of color into an RCT of RBSTE, (2) to understand Veterans' views of the acceptability and appropriateness of intervention content and provider behavior and the feasibility of participation in a future RCT; and (3) to refine a holistic assessment strategy.

**Figure 1.** Schematic of study activities

Veterans who express interest in study participation will be contacted by study staff and provided with general information about the study. Those who continue to be interested will engage in the informed consent process in person or using remote procedures (e.g., VA Docusign), depending on personal and health considerations. Veterans who provide written consent will go on to complete the baseline assessment (refer to **Assessment approach**). Randomization will occur at the group level: once a cohort of 4-10 Veterans has enrolled and completed the baseline assessment, the cohort will be randomized by the study statistician. Although group randomization has disadvantages as compared to individual randomization (e.g., dependence among group members, lack of blinding of the final 1-2 groups), these can be managed and are outweighed in our experience by facilitating recruitment because groups can begin more quickly. Groups will meet in **weekly 90-minute sessions for 8 weeks**. Videoconferencing will be used to minimize barriers to participation, including transportation and public health concerns. The assessment battery will be repeated at the end of the group. Participants will be compensated \$50 for each assessment point for total compensation of \$100.

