**Assessment approach.** Because of the history of human rights violations and misconduct in medical and psychological research, many people of color mistrust research activities (Suite, La Bril, Prim, & Harrison-[name], 2007). This is an important reason to study the feasibility of the proposed data collection strategy and motivation to prioritize brevity of our assessment battery. A record of study participation will be gathered following CONSORT guidelines to quantify enrollment and retention. Assessments will be completed within 1 month prior to the beginning of group and within 1 month after the end of group. The sample will be characterized at the baseline assessment. Participant characteristics including age, gender, race/ethnicity, education, work status and financial and housing stability, will be gathered using a demographic questionnaire. Adherence to group will be quantified based on attendance at sessions and proportion of homework completed (**coded as none/partial/complete as judged by the therapist**).

**Recruitment feasibility.** Aim 1 of this study involves evaluating strategies for recruiting VOC for this type of study. *Enrollment rate*, defined as the number of contacts per enrollment, will be used to optimize the future approach to accrual. There is no target enrollment rate as many can be acceptable; this metric will serve to guide resource allocation. **Gathering information from Veterans and providers about reasons for declining participation or referral, however, will be important in determining the representativeness of the sample.** *Number of enrollments per month* will be viewed as successful if at least four individuals are enrolled per month as that level of recruitment represents a reasonable period (average 2-3 weeks) for a Veteran to wait for a group to begin. *Initiation rate* will be defined as the proportion of Veterans who initiate the intervention among all consented participants. This will inform recruitment strategies (i.e., which strategies lead to the highest proportion of treatment initiation) but also may help to identify areas of improvement in terms of connecting Veterans to the project. As these behaviors are recorded prior to the first session, we do not expect group differences.

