**Acceptability, appropriateness and feasibility.** Relevant to aim 2, participant behavior is one important marker of participants' perceptions of the project and their ability to comply with research procedures. *Retention rate* will be defined as the percent of enrolled sample completing all assessment time points; at least 80% completion will be considered successful. *Per protocol completion rate* will be defined as the proportion of subjects who complete 6 or more sessions among those who initiate treatment; at least 90% completion will be considered successful. *Intent-to-treat completion rate* will be defined as the proportion of subjects who complete 6 or more sessions of intervention among all randomized subjects; at least 80% is the target. *Compliance with homework* will be assessed with a goal of at least 80% moderately or fully complete (refer to **Assessment approach**). In addition, Veterans will be directly queried about their experience using the *Acceptability of Intervention Measure (AIM)*, *Intervention Appropriateness Measure (IAM)*, and *Feasibility of Intervention Measure (FIM)*. The 5-item measures have strong content validity, test-retest reliability and sensitivity to change (Weiner et al., 2017). The psychotherapy version of the *Provider Rating Scales*, which were previously used to assess perceptions of VA mental health providers (Spoont et al., 2017), will be used to assess Veterans' perceptions of the group leader. Between-group differences on these measures would likely reflect the difference in content between the two groups.

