**Sample size.** As a feasibility study, the decision about sample size is not about establishing sufficient power to detect change in clinical outcomes but rather about demonstrating the viability of a future larger-scale study. The sample size was determined based on practical and quantitative considerations. We will aim for enrollment of 4 groups of each type of intervention, each with approximately 6 Veterans (average 6, range 4-10), leading to a total sample size of approximately 48 (24/cell) in the 15-month recruitment period. This rate of enrollment would demonstrate feasibility of a larger future study in that we would demonstrate that a steady flow of adequately sized intervention groups can be recruited. Given that this is a pilot and feasibility study, we are looking for clinical signal and feasibility rather than examining efficacy. All sample size analyses were performed using statistical package R. A two-sided type I error of 0.05 was assumed.

The sample size assessment was conducted for assessing the enrollment and completion rates. First, we assessed the precision of estimates based on projected sample size. We considered a range of target rate from 0.60 to 0.90 and estimated the width of the 95% exact binomial confidence interval for enrollment and completion rates for overall and for each intervention group (see **Table 1**).

**Table 1.** The width of 95% confidence intervals for enrollment and completion rates

Sample size	Estimated rate						
	0.60	0.65	0.70	0.75	0.80	0.85	0.90
48	0.267	0.261	0.251	0.239	0.222	0.201	0.174
24	0.365	0.357	0.345	0.329	0.308	0.282	0.249

From **Table 1**, if an estimated intervention initiation rate is 0.80, a sample size of 48 (total) and 24 (per intervention group) will produce a two-sided 95% confidence interval with a width of 0.222 and 0.308,

respectively. If an estimated intervention initiation rate is 0.90, the width of the 95% CI is reduced (becomes more precise, see **Table 1**) with the same sample size projected above.

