As a feasibility study, the sample size was not projected to ensure enough study power for hypothesis testing. We assessed the effect size of the outcome (such as Brief PHI, DASS-21, TSDS) that can be detected with the planned sample size and 80% power. The effect size for change in outcome from baseline to post treatment in each intervention group and overall was estimated based on a paired t-test. With a sample size of 24 per group and 48 in total, we could detect an effect size of 0.60 and 0.41, which are moderate effect sizes. To compare the outcome change between the RBSTE and PCT groups, with 24 per group, we could detect a moderate effect size of 0.83 for the difference with 24 subjects per group. This effect size would be clinically meaningful thus signaling the need for additional study.

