We will assess four outcome measures for enrollment and retention: 1) *enrollment rate* defined as the proportion of consented subjects among all screened and eligible patients; 2) *initiation rate* defined as the proportion of subjects who initiate the intervention among all consented subjects; 3) *per protocol completion rate* defined as the proportion of subjects who complete 5 or 6 sessions of intervention among those who start the intervention; 4) *intent-to-treat completion rate* defined as the proportion of subjects who complete 5 or 6 sessions of intervention among all randomized subjects. The 95% CI (based on normal approximation or exact binomial test when appropriate) will be estimated for all these rates for overall and by each intervention group. The rates for the RBSTE and PCT groups will be compared by Fisher's exact test. Multivariable analysis will be also performed to examine the difference in outcomes between intervention groups using logistic regression.

**Aim 2:** *To understand Veterans' views of the acceptability and appropriateness of treatment content, the feasibility of participation, and perceptions of provider behavior and attitudes.*

The AIM, IAM, FIM and Provider Rating Scales will be estimated by mean, SD and 95% CI. Intervention groups will be compared by Wilcoxon rank sum test. Multivariable analysis will be also performed to examine the difference in outcomes between intervention groups using linear regression.

**Aim 3:** *To optimize the strategy for holistic evaluation of intervention effects.*

As aforementioned, we will include a comprehensive list of cardiometabolic, neuroendocrine, and inflammatory markers that had been shown as reliable markers of AL in the literature to derive an AL index for each participant. We hypothesize that AL index at baseline will be associated with perceived discrimination as well as other psychosocial outcomes and that pre to post-intervention changes of AL index will differ between the two groups. We will perform regression analysis and variable selection using LASSO (Tibshirani 1996) to identify a smaller subset of the AL markers at baseline that show significant associations with psychosocial outcome measures. The effect size for pre and post change in AL markers will be estimated. This will inform future efficacy and effectiveness studies in potential reduction of a list of biomarkers to enhance feasibility, efficiency and reduce participant burden.

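### Attendance is compared between arms only as yes/no rates; a difference in sessions attended that accounts for therapy group would use the data somewhat better

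*Combined protocol and SAP*

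**What the plan says.** All places are in the Combined protocol and SAP, Research Design and Methods.

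- **Sessions offered.** Groups meet in "weekly 90-minute sessions for 8 weeks", so a Veteran can attend 0 to 8 sessions. Cohorts of 4-10 Veterans are randomized as a whole.
- **What is recorded (Assessment approach).** "Adherence to group will be quantified based on attendance at sessions and proportion of homework completed".
- **Success thresholds (Acceptability, appropriateness and feasibility).** Intent-to-treat completion is the "proportion of subjects who complete 6 or more sessions of intervention among all randomized subjects; at least 80% is the target". The per protocol rate uses the same cut among those who start, with a 90% target.
- **Between-arm analysis (Analyses, Aim 1).** "The rates for the RBSTE and PCT groups will be compared by Fisher's exact test". The rates concerned include initiation and the two completion rates. A multivariable logistic regression of the same yes/no outcomes is added. Here completion is defined as 5 or 6 sessions, not 6 or more.
- **Contrast with Aim 2.** The questionnaire scales are kept as scores, with mean, SD and 95% CI, a Wilcoxon test and linear regression.
- **Status of tests.** The Sample size section says that the study was not sized for hypothesis testing. The Analyses section compares arms only where this is judged necessary and appropriate.

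**The concern.** The completion cut serves as a feasibility threshold, but as an arm comparison it is coarse. A Veteran who leaves after one session counts the same as one who attends five, and six sessions count the same as eight. Attendance is one of the plan's behavioural markers of how Veterans view the project, yet it is the marker reduced to yes/no, while the scales beside it are analysed as scores. No reason is given.

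At stake is how precisely the pilot can describe a difference in attendance between RBSTE and PCT, and whether it leaves an estimate in sessions for planning the larger trial. The cut is also unsettled, because the two sections define completion differently. Read literally, 5 or 6 sessions excludes Veterans who attend 7 or 8.

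**Working it through.** **Inputs from the documents.** "A two-sided type I error of 0.05 was assumed"; sample size "leading to a total sample size of approximately 48 (24/cell) in the 15-month recruitment period"; 4 groups per arm averaging 6 Veterans; 8 sessions. The attendance distribution and the within-group correlation (ICC) are not given, so ranges are assumed below.

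**1. The plan's own figure.** The plan assesses the effect that "can be detected with the planned sample size and 80% power" and concludes that "we could detect a moderate effect size of 0.83 for the difference with 24 subjects per group". For a two-sample t-test with 46 df, power = P(T > t(0.975, 46)) with noncentrality d × √(24/2). Solving for 80% gives d = 0.826, so 0.83 reproduces (power at 0.83 is 0.804). This assumes independent Veterans. The plan gives no power figure for the comparison of completion rates.

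**2. Fisher's test on the cut, 24 independent Veterans per arm.** Power = Σ Bin(x; 24, p1) × Bin(y; 24, p2) over all tables (x, y) with Fisher p ≤ 0.05.

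| Completion | Fisher rejection rate |
|---|---|
| 80% vs 80% | 0.026 |
| 90% vs 90% | 0.017 |
| 80% vs 60% | 0.236 |
| 90% vs 70% | 0.314 |
| 80% vs 50% | 0.493 |
| 90% vs 60% | 0.602 |

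Power of 80% needs about 80% vs 38%, or 90% vs 52%.

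**3. The count, still with independent Veterans.** Simulated 0-8 counts were calibrated to the same completion rates. If attendance shifts across the range (beta-binomial or steady drop-out), Wilcoxon power at 80% vs 60% is 0.39-0.49. Not all of the gap to Fisher is due to the cut. The uncorrected two-proportion test has 0.323, so 0.323 − 0.236 = 0.087, about 9 points, is Fisher's conservatism. That leaves about 0.39 − 0.32 = 0.07 to 0.49 − 0.32 = 0.17 for the cut. If the arms differ only in the chance of crossing the cut, the count does no better, or worse: 0.22-0.23 against Fisher's 0.24 at 80% vs 60%, and 0.45 against 0.60 at 90% vs 60%. In that case the spread of counts on either side of the cut adds noise and no signal.

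**4. Group randomization.** The design effect is 1 + (6 − 1) × ICC. ICC 0.05, 0.10 and 0.20 give 1.25, 1.5 and 2.0, so 24 Veterans per arm carry the information of 19.2, 16 and 12. With 4 groups of 6 per arm, a t-test on group means has 8 − 2 = 6 df. Simulated power:

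| Contrast | ICC | Mean sessions | Completer rate | Gain |
|---|---|---|---|---|
| 80% vs 50% | 0 | 0.59 | 0.50 | 0.09 |
| 80% vs 50% | about 0.04 | 0.46 | 0.40 | 0.06 |
| 80% vs 50% | about 0.13 | 0.31 | 0.29 | 0.02 |
| 80% vs 60% | 0 | 0.34 | 0.27 | 0.07 |
| 80% vs 60% | 0.03 | 0.29 | 0.25 | 0.04 |
| 80% vs 60% | 0.09 | 0.25 | 0.23 | 0.02 |
| 80% vs 60% | 0.17 | 0.20 | 0.18 | 0.02 |

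In the third row the group effects pulled realized completion to about 77% vs 50%; both analyses used the same data. Under no difference, the group-mean test rejected in 0.048-0.050 of trials for the count and 0.056-0.057 for the completer rate. Over a wider set of assumed patterns the gain was about 1 to 13 points.

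**5. Ignoring groups.** Under no difference, a Wilcoxon test on the count rejects in 0.078 of trials at ICC about 0.04 and 0.135 at about 0.13. Fisher's test rejects in 0.039 and 0.071. A Welch test on the count reached 0.06-0.18 with modest to strong group effects, against 0.03-0.09 for Fisher.

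**The case against.** The strongest reply is that little hangs on this comparison. The study is declared unpowered for tests, the primary analysis is overall and within arm, completion is a benchmark with targets and CIs, and no decision depends on the Fisher p-value. Acceptability is also measured by the AIM, IAM and FIM. A descriptive summary of sessions by arm would be compatible with the plan as it stands. All of this stands, and it makes the point minor. It does not remove it: Aim 1 says that the rates will be compared, and names no comparison of the count.

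A reader might also infer that much of the information is lost, since Fisher has 24% power at 80% vs 60% and a test on the count 39-49%. The documents do not support this. The figures assume independent Veterans although cohorts are randomized, about 9 points of the gap come from the choice of test, and the attendance pattern is unknown.

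Nor does it follow that a plain Welch or Wilcoxon test on the count would be an improvement. With within-group correlation its false-positive rate rises further above 5% than Fisher's. Fisher's conservatism is itself a property under independence.

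Finally, that a full count exists for every Veteran is a reasonable inference from the Assessment approach, not something the text states.

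**Conclusion.** The point holds in a limited form. Every between-arm attendance analysis named in Aim 1 is yes/no, and this discards some information. With therapy group as the unit, analysing the count gains about 1 to 13 points of power over the completer rate when attendance shifts across the range. It gains nothing, or loses, when the arms differ only at the cut. This rests on 4 equal groups of 6 per arm and on assumed attendance patterns and ICCs. The range describes those scenarios and is not a bound. Power stays low either way: at 80% vs 60% it is 0.20-0.34 for the count.

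The better reasons to change are that the result is an estimate in sessions with a CI, which suits a hypothesis-generating pilot, and that it does not depend on which completion definition prevails. Severity is minor.

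**What to change.** In Analyses, Aim 1:

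1. Keep the completion rates with 95% CIs, judged against the 80% and 90% targets.
2. Add, as the between-arm attendance comparison, the difference in mean sessions attended (0-8) in all randomized Veterans, with non-starters scored 0. Give a 95% CI and a test that account for therapy group, for example a t-test on group means or a mixed model with a random group effect and small-sample degrees of freedom. Non-starters can be included because their cohort is fixed at randomization.
3. Do not use a Welch or Wilcoxon test that ignores groups. Show Fisher's test on the rates as supportive.
4. Reconcile the completion definitions in the Acceptability, appropriateness and feasibility section and in Aim 1.

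The cost is a sentence or two of analysis wording and one line of output, with no new data if attendance is logged by session, and no more Veterans. The downsides are that the comparison is stated in sessions rather than in the rate used for the targets, and that its precision is limited by about 4 groups per arm. The change should be made before attendance data are seen by arm.

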**Participants.** Veterans ( $n \approx 48$ , potential range 24-60) will be recruited from medical (e.g., primary care) and mental health programs throughout the facility and from the community. Given the feasibility aim of this project, ability to participate is intentionally broad to demonstrate demand and maintain ecological validity. Thus, inclusionary criteria are as follows: (1) self-identified as a BIPOC, (2) Veteran, (3) age 18 or older, (4) able to consent to study activities, and (5) endorsing one or more perceived discrimination experiences on the *Everyday Discrimination Form* (short version) or the *Major Experiences of Discrimination Scale* (abbreviated version; Sternthal, Slopen & Williams, 2011) "a few times a year" or more frequently and endorsing stress on a validated single-item measure (Elo, Leppanen, & Jahkola, 2003). Exclusionary criteria include: (1) serious mental illness, alcohol/substance use disorders, or cognitive impairment that may interfere with the ability to benefit from group (e.g., severe depression, psychotic illness, mania, dementia, **untreated** alcohol/substance dependence); and (2) serious suicidality or homicidality (e.g., ideation with plan/intent) that is likely to require urgent/emergent intervention within the study period.

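### The adjusted logistic comparison of arms on completion would rest on about 4 to 10 non-completers, so its odds ratio will be very imprecise and, at the 90% target, sometimes not estimable

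*Combined protocol and SAP*

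**What the plan says.** All references are to the combined protocol and SAP, Research Design and Methods.

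- **Analyses, Aim 1.** Four rates are listed, including per-protocol and intent-to-treat completion. The arms are compared by Fisher's exact test, and then: "Multivariable analysis will be also performed to examine the difference in outcomes between intervention groups using logistic regression". No estimator is named.
- **Analyses, opening paragraph.** Covariates are candidates if associated with the outcome or unbalanced between arms at p < 0.15, and are kept by backward elimination at p < 0.10. There is no limit on their number, no minimum event count and no rule for zero cells. Multivariable modelling is made conditional on being appropriate, without a criterion.
- **Acceptability, appropriateness and feasibility.** The intent-to-treat rate counts those "who complete 6 or more sessions of intervention among all randomized subjects; at least 80% is the target". The per-protocol rate is "among those who initiate treatment; at least 90% completion will be considered successful".
- **Sample size.** "We will aim for enrollment of 4 groups of each type of intervention", about 6 Veterans each, "leading to a total sample size of approximately 48 (24/cell) in the 15-month recruitment period". The Participants paragraph gives "potential range 24-60".
- **Design.** "Randomization will occur at the group level".

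**The concern.** In logistic regression the information comes from the rarer outcome, here the Veterans who do not complete. The targets are minimums, so a program that does well leaves few of them, and one that does better leaves fewer. An uncapped set of covariates is then fitted to a handful of events.

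Two things can follow. The odds ratio may be finite but so imprecise that it says almost nothing. Or one arm may have no non-completers, in which case the maximum-likelihood log odds ratio for arm does not exist and a Wald p-value drifts towards 1 whatever the data show. At stake is the adjusted comparison only. Without a rule set in advance, the analyst would have to choose a fallback after seeing the data.

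**Working it through.** **Planned size.** 2 arms x 4 groups x 6 Veterans = 48, or 24 per arm, which reproduces the plan's figure. The plan gives no figure for the logistic model; Table 1 concerns the precision of single rates.

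**Expected non-completers = N x (1 - rate).**
- Intent-to-treat at 80%: 48 x 0.20 = 9.6.
- Per protocol at 90%, everyone initiating: 48 x 0.10 = 4.8.
- Per protocol at 90%, with the initiation rate implied by the two targets (0.80/0.90): 48 x 0.889 = 42.7 starters, so 4.3.
- Per protocol at 90%, with 80% initiation (an illustrative value in Sample size): 38.4 starters, about 19 per arm, so 3.8.

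**Events per parameter**, for arm plus 1 to 3 covariates (2 to 4 parameters, intercept not counted): 9.6/2 = 4.8 down to 9.6/4 = 2.4 at the 80% target; 4.3/2 = 2.1 down to 4.3/4 = 1.1 at the 90% target.

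**Imprecision without any covariates**, 24 per arm, with a and b non-completers in the two arms. SE of the log odds ratio = sqrt(1/a + 1/(24-a) + 1/b + 1/(24-b)); ratio of upper to lower 95% limit = exp(2 x 1.96 x SE).

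| Non-completers | SE | Upper/lower ratio |
|---|---|---|
| 5 v 5 | 0.711 | 16 |
| 2 v 3 | 0.963 | 44 |
| 2 v 2 | 1.044 | 60 |

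With 5 v 5 the interval runs from 0.25 to 4.0; with 2 v 2, from 0.13 to 7.7.

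**Chance that at least one arm has no non-completers** = 1 - (1 - p^n)^2, where p is the true completion rate in both arms and n the number per arm, taking Veterans as independent.

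| n per arm | p = 0.80 | p = 0.90 |
|---|---|---|
| 24 (N = 48) | 0.9% | 15% |
| 22 | 1.5% | 19% |
| 19 | 2.9% | 25% |
| 12 (N = 24) | 13% | 49% |
| 30 (N = 60) | 0.2% | 8% |

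Example: 0.9^24 = 0.0798, and 1 - (1 - 0.0798)^2 = 0.153. If the rates differ, at 95% and 85% with 22 per arm, the chance is 1 - (1 - 0.95^22)(1 - 0.85^22) = 34%. In simulation with an assumed group-level ICC of 0.10 and N = 48, the chance is about 4% at 80% and 23% to 28% at 90%.

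**The plan's selection rule**, simulated at N = 48 with eight assumed baseline variables unrelated to the outcome: the model at entry had at least one non-finite coefficient in 9% of data sets at 80% completion and 26% at 90%. Where it was finite, the median upper/lower ratio for the arm odds ratio was 21 and 60.

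**What separation looks like.** With 0/24 v 5/24 non-completers, Fisher's exact p = 0.0496, while a maximum-likelihood logistic fit gives a Wald p of about 0.999. The plan would report both.

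**The case against.** The case on the other side has real force.

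- **Fisher's exact test is prespecified and copes with zero cells.** This stands. A reader might infer that the arm comparison as a whole is lost under separation. It is not: the unadjusted comparison remains usable (clustering apart), and only the adjusted supplement is affected. Fisher's test does not, however, supply an adjusted estimate.
- **Modelling is conditional on being appropriate, and no estimator is named.** This stands in part. The condition has no criterion, the Aim 1 sentence does not repeat it, and logistic regression without further description is normally read as maximum likelihood.
- **A reader might infer that the odds ratio will often be infinite.** The plan's figures do not support that generally. At the 80% target with 24 per arm the chance is about 1%; it becomes material at the 90% target or at small N. Sample size also considers rates down to 0.60, where 48 Veterans would give 48 x 0.40 = 19.2 non-completers.
- **Higher failure rates can be produced by forcing in covariates.** With arm plus three assumed covariates (two binary, one continuous), 55% of simulated data sets at 90% completion have some non-estimable coefficient. That counts any coefficient, not the arm odds ratio, and bypasses the plan's own selection, so it does not measure this problem.
- **The stakes are modest.** This stands. The primary analysis is described as estimation overall and within each arm, the plan disclaims power for hypothesis tests, and the success thresholds use no arm comparison.

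**Conclusion.** The concern holds as one of imprecision at both targets and of occasional non-estimability at the higher one. With 48 Veterans and about 10 or 4 to 5 non-completers, the adjusted odds ratio will be close to uninformative. The maximum-likelihood arm odds ratio is infinite or undefined in about 15% to 25% of trials at 90% completion with 19 to 24 per arm, and in about 1% at 80% with 24 per arm.

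These chances assume equal true rates in both arms and independent Veterans; the number of starters is inferred from the targets or from an illustrative initiation rate, since the plan sets no initiation target. The ICC and the simulated covariates are assumptions too. The event counts also depend on which completion definition applies: the targets are set for 6 or more sessions, whereas Aim 1 analyses 5 or 6.

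This is a secondary analysis and decides no feasibility criterion. It is worth correcting because the correction is cheap, not because the trial's conclusions depend on it.

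**What to change.** For the two completion rates only:

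1. Next to Fisher's test, report the RBSTE minus PCT risk difference with a score-based 95% CI.
2. Either drop the adjusted completion model, or fit it by Firth penalized (or exact) logistic regression with arm and at most one covariate named in advance, without data-driven selection.
3. State that these intervals ignore clustering by cohort and may be too narrow, since whole cohorts are randomized.
4. Reconcile the completion definitions in the feasibility and Aim 1 paragraphs, because they change the event count.

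The change should not be extended to the enrollment rate. Randomization follows consent and baseline, so eligible Veterans who decline belong to no arm and an arm difference is undefined.

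The cost is SAP wording and standard R packages, with no extra participants, visits or data. The downside is less covariate adjustment in the completion model.
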